**Table 5: Criteria for Defining Dose-Limiting Toxicities**

Toxicity
Hematologic Toxicities: 
 
Any Grade 4 thrombocytopenia or neutropenia lasting > 7 days
 

Nonhematologic Toxicities: 
 
Any Grade 4 toxicity
 
Any Grade 3 or 4 AST, ALT, or total bilirubin elevation
 
Any other Grade 3 toxicity EXCLUDING:           
 
Nausea/vomiting controlled by medical intervention within 72 hours
 
Grade 3 rash in the absence of desquamation, no mucosal involvement, does not require systemic steroids, and resolves to Grade 1 by the next scheduled dose of MK-3475 or 14 days, whichever is longer.
 
 
 
Episcleritis, uveitis, or iritis of Grade 2 or higher
 

General: 
 
If subjects are unable to receive 75% of INCB024360 or 2 doses of MK-3475 during the DLT observation period because of toxicity, even if the toxicity does not meet DLT criteria defined above.
 
Greater than 2 week delay in starting Cycle 3 because of a treatment-related toxicity, even if the toxicity does not meet DLT criteria defined above.
 

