In this current, ongoing study (INCB 24360-202), enrollment is complete in the epacadostat 25 mg BID, 50 mg BID, and 100 mg BID cohorts with pembrolizumab 2 mg/kg IV Q3W as well as in the Phase 1 expansion cohorts of epacadostat 50 mg BID, 100 mg BID, and 300 mg BID with pembrolizumab 200 mg IV Q3W. The Phase 2 portion of the study is ongoing, in which the recommended Phase 2 dose of epacadostat 100 mg BID is being evaluated in combination with the fixed dose of pembrolizumab 200 mg IV Q3W. As of 27 FEB 2017, a total of 356 subjects have been enrolled. The update below includes safety in the combined Phase 1 and Phase 2 treatment groups treated with epacadostat 100 mg BID in combination with pembrolizumab in this study who had at least 1 month of safety data available.

Among the 294 subjects who have received epacadostat 100 mg BID in combination with pembrolizumab in Phase 2, the most frequently reported ( $\geq 10\%$ ) treatment-related AEs of any grade for the combined Phase 1 and Phase 2 treatment groups were fatigue (29%), rash (17%), nausea (11%), and pruritus (10%). Fatigue (29%) and rash (17%; including the preferred terms rash, rash maculopapular, rash generalized, rash macular, and rash pruritic) were the only treatment-related AEs reported in  $> 15\%$  of subjects ([Hamid et al 2017](#)). Treatment-related AEs of rash were only reported in the Phase 2 group.

The ORR in 19 evaluable subjects with treatment-naïve metastatic melanoma was 53% (10/19), with disease control rate of 74% (14/19). Median PFS has not been reached and all responses are ongoing with minimum follow-up of 31.7 weeks. Objective responses were also seen in other tumor types enrolled in Phase 1 ([Gangadhar et al 2015](#)). Additional data were recently presented

confirming an ORR and DCR in subjects with treatment-naïve metastatic melanoma of 58% (11/19) and 74%, respectively ([Gangadhar et al 2016](#)).

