#### 4.1.1. Phase 1 Dose-Escalation Design

Phase 1 is the dose-escalation phase, which will include cohorts of subjects treated with INCB024360 BID at initial doses of 25 mg BID, 50 mg BID, and 100 mg BID in combination with MK-3475 2 mg/kg Q3W, and INCB024360 300 mg BID in combination with MK-3475 200 mg/kg Q3W. Interim dose levels of 75 mg QD (50 mg in the morning/25 mg in the evening), 75 mg BID, or 200 mg BID may be evaluated if DLTs occur at 50 mg BID, 100 mg BID, or 300 mg BID following the review of available safety data at the Dose Escalation/Cohort Review meetings. One treatment cycle of MK-3475 administered Q3W will consist of 21 days. A minimum of 3 subjects will be enrolled and treated in each cohort, and all 3 subjects will be observed for a minimum of 42 days (6 weeks) before the subsequent cohort begins enrollment. Subjects must have received the cohort-specific dose of INCB024360 for at least 80% of the doses during the 42-day DLT observation period, and must have received 2 doses of MK-3475 during that 42-day period, or must have experienced a DLT to be included in the cohort review for DLTs. Additional subjects will be enrolled in a cohort to achieve the minimum of 3 evaluable subjects if dropouts or dose interruptions or reductions occur that result in a subject being nonevaluable for DLTs. When the preliminary safety of 50 mg BID and 100 mg BID has been established, additional subjects with melanoma will be enrolled at 50 mg BID for a total of 9 subjects. An additional safety cohort will also be opened at 100 mg BID in parallel to 300 mg BID being tested. This may also be limited to subjects with melanoma, NSCLC, or specific cancer types from among those included in Phase 1 at the sponsor's discretion. If 300 mg BID is also determined to be well tolerated, an additional safety cohort may also be enrolled that, at the sponsor's discretion, may be limited to specific cancer types from among those included in Phase 1. The RP2D will be selected from the evaluated safety expansions. All subjects in these safety expansions will be treated with MK-3475 200 mg Q3W.

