**3 + 3 + 3 Design:** The dose of INCB024360 will be escalated if 0 of the first 3 evaluable subjects enrolled experience a DLT. If > 1 of the first 3 evaluable subjects enrolled experience a DLT, the prior dose level will be considered the MTD. If 1 of the first 3 evaluable subjects enrolled experience a DLT, the cohort will be expanded to include 3 additional evaluable subjects. If 1 of the 6 evaluable subjects enrolled in the expanded cohort experience a DLT, dose escalation to the next dose level may occur. If 2 of 6 subjects experience a DLT that cohort will be expanded to 9 subjects. If  $\geq 2$  of 3, 3 of 6, or 3 of 9 subjects experience DLTs within a cohort, then that dose level will be determined to have exceeded the MTD and the prior dose level will be considered the MTD or an intermittent dose may be tested.

For the safety expansion cohorts, if < 4 of the first 9 evaluable subjects experience a DLT at the given dose level, the dose will be deemed tolerable. If  $\geq 4$  of the first 9 evaluable subjects experience a DLT in the safety expansions, then the next lower dose level of INCB024360 will be deemed the RP2D. The RP2D will be selected from one of the doses deemed tolerable (as defined above).

If at least 25 mg BID cannot be combined safely with MK-3475 2 mg/kg, other alternative dose schedules (ie, intermittent dosing) of INCB024360 may be tested, if needed, following the review of available safety data at the Dose Escalation/Cohort Review meetings. If an alternate schedule is tested and determined to be safe, re-escalation of INCB024360 according to [Table 1](#) will proceed with MK-3475 2 mg/kg Q3W.

The cohorts and dose levels are shown in [Table 1](#) for the dose escalations of INCB024360 with Q3W schedule of MK-347 and in [Table 2](#) for the safety expansions cohorts.

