**5.5.2. Procedures for Cohort Review and Dose Escalation in Phase 1**

Telephone conferences will be scheduled by the sponsor with Phase 1 investigators in order to review cohort-specific data, overall safety data from prior cohorts (if applicable), and to agree on dose escalation. For additional safety oversight, this group will review and adjudicate individual high-grade AEs as potentially dose-limiting and for guiding the study team on decisions regarding dose escalation and cohort expansion. The same method will be used for reviewing data at the end of Phase 1 to determine the recommended dose for Phase 2.

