**Table 6: Dose Modification Guidelines for Drug-Related Adverse Events**

Toxicity	Grade	Hold Treatment (Y/N)	Timing for Treatment Restart	Dose/Schedule for Treatment Restart		Discontinue Subject (After Medical Monitor Consultation)
				INCB024360	MK-3475	
Hematologic toxicity	1, 2	No	N/A	N/A	N/A	N/A
	3	Yes	Toxicity resolves to $\leq$ Grade 1 or baseline	Restart at same dose	Restart at same dose and schedule. See Section 5.6.3 for recommendations regarding immune-mediated AEs.	Toxicity does not resolve within 12 weeks of last infusion.
	4	Yes	N/A	N/A	N/A	Permanently discontinue
Nonhematologic toxicity Note: Exception to be treated to similar Grade 1 toxicity: – Grade 2 alopecia – Grade 2 fatigue – Grade 3 rash in the absence of desquamation, no mucosal involvement, does not require systemic steroids, and resolves to Grade 1 within 14 days For additional information regarding AEs with potential immune etiology, see Section 5.6.3 or for subjects with HCC, refer to Appendix J for guidance related to hepatic adverse events.	1	No	N/A	N/A	N/A	N/A
	2	Consider holding for persistent symptoms	Toxicity resolves to $\leq$ Grade 1 or baseline	Restart at same dose	Restart at same dose and schedule. See Section 5.6.3 for recommendations regarding immune-mediated AEs.	Toxicity does not resolve within 12 weeks of last infusion
	3	Yes	Toxicity resolves to $\leq$ Grade 1 or baseline	Restart at 1 dose level lower.	Restart at same dose and schedule. See Section 5.6.3 for recommendations regarding immune-mediated AEs.	Toxicity does not resolve within 12 weeks of last infusion. Permanent discontinuation should be considered for any severe or life-threatening event.
	4	Yes	N/A	N/A	N/A	Permanently discontinue

Note: Subjects who experience a recurrence of the same severe or life-threatening AE at the same grade or greater with rechallenge of the combination should be discontinued from study treatment. For toxicities such as recurrent or intolerant rash with this combination, subjects may have the opportunity to resume treatment with MK-3475 alone with medical monitor approval.

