**Table 8: Dose Modification and Toxicity Management Guidelines for Immune-Related Adverse Events (Continued)**

Toxicity	Grade	Study Treatment	Action Taken	AE Management	Monitor, Follow-up and Restart Guidelines
All Other Drug-Related Toxicity	Intolerable/ persistent Grade 2	MK-3475	Withhold until Grade 0-1	Based on severity of AE administer corticosteroids	
 
Ensure adequate evaluation to confirm etiology or exclude other causes
 

		INCB024360	Withhold until Grade 0-1  Once resolved to Grade 0-1, may restart: Related: Reduce by 1 dose level. Not Related: Same dose level.		
	Grade 3	MK-3475	Withhold until Grade 0-1, or discontinue based on the type of event. Events that require discontinuation include and not limited to: Gullain-Barre, encephalitis		
		INCB024360	Withhold until Grade 0-1  Once resolved to Grade 0-1, may restart: Related: Reduce by 1 dose level. Not Related: Same dose level.  Events that require discontinuation include and not limited to: Gullain-Barre, encephalitis		
	Grade 4 or recurrent Grade 3	MK-3475	Permanently discontinue		
		INCB024360	Permanently discontinue		

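### The 80% evaluability rule and the 75% dose-loss DLT rule do not meet, so a subject limited by toxicity can be replaced and drop out of the DLT denominator

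*Protocol*

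**What the plan says.** Protocol 4.1.1 sets the exposure needed to enter the DLT review: "Subjects must have received the cohort-specific dose of INCB024360 for at least 80% of the doses during the 42-day DLT observation period". Two MK-3475 doses are also needed. The alternative route into the review is to have had a DLT. Further subjects are enrolled when dropouts occur, or when "dose interruptions or reductions occur that result in a subject being nonevaluable for DLTs". That text makes no exception for interruptions or reductions caused by toxicity. The escalation rule then works on evaluable subjects only; for example, the dose goes up "if 0 of the first 3 evaluable subjects enrolled experience a DLT". SAP 3.1 repeats all of this.

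Protocol Table 5, under its general criteria, makes toxicity-driven dose loss a DLT even when the toxicity meets no other criterion: "If subjects are unable to receive 75% of INCB024360 or 2 doses of MK-3475 during the DLT observation period because of toxicity". SAP Table 3 has the same rule. The MK-3475 parts of the two rules agree, at two doses each. The epacadostat parts do not: one is 80% of doses at the cohort dose, the other is 75% with no basis stated.

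**The concern.** The two rules should leave a toxicity-limited subject in one of two states: enough drug taken to be counted, or so little taken because of toxicity that the subject is a DLT. Between the thresholds there is a third state, in which the subject is non-evaluable and another is enrolled instead. A subject who dropped out for unrelated reasons can be replaced without bias. A subject whose doses were held for toxicity cannot, because the reason for leaving the denominator is the outcome being measured. DLTs are part of the Phase 1 primary objective, and Protocol 5.5 says that toxicities in the first 42 days define tolerability.

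**Working it through.** The plan states no figure for this gap, so there is none to reproduce. The check is a count of doses.

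**Planned doses.** Twice daily for 42 days: 42 x 2 = 84.

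**Thresholds, taking 75% as a dose count.**
- Evaluable without a DLT: 0.80 x 84 = 67.2, so at least 68 doses at the cohort dose (68/84 = 81.0%).
- Dose-loss DLT: 0.75 x 84 = 63, so 62 doses or fewer because of toxicity (62/84 = 73.8%).
- Neither: 63 to 67 doses (63/84 = 75.0%; 67/84 = 79.8%).
- Missed doses in the gap: 84 - 67 = 17 to 84 - 63 = 21, that is 8.5 to 10.5 days.

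**Can a subject get there without another DLT?** Yes, under the current text. For a Grade 2 nonhematologic event, Protocol Table 6 says "Consider holding for persistent symptoms", with restart at the same dose. It also holds treatment for Grade 3 hematologic toxicity, again with restart at the same dose. Neither grade is in itself a Table 5 DLT. A hold of 8.5 to 10.5 days does not by itself produce the delay of more than two weeks in Cycle 3 that Table 5 counts.

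**Dose reductions.** Evaluability counts doses at the cohort dose. If the 75% counts doses at any level, a reduced subject can fail the first test and pass the second. Illustration: 56 doses at the cohort dose, 22 at a lower level and 6 missed.
- At the cohort dose: 56/84 = 66.7%, so not evaluable.
- At any level: (56 + 22)/84 = 78/84 = 92.9%, so no dose-loss DLT.
- If the 75% were also counted at the cohort dose, the same subject would be a DLT at 66.7%, provided the cause was toxicity.

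The current Table 8 provides for such reductions, for instance after an intolerable or persistent Grade 2 event: "Once resolved to Grade 0-1, may restart: Related: Reduce by 1 dose level". This shows that the missing basis matters. It is not a measure of what happened in Phase 1.

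**Possible effect on the DLT rate.** Evaluable counts and DLTs are from Protocol 1.4.2, taking one DLT per subject. One gap subject at each dose is an assumption.

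| Dose | As reported | Gap subject as DLT | Gap subject as evaluable non-DLT |
|---|---|---|---|
| 50 mg BID | 2/19 = 10.5% | 3/20 = 15.0% | 2/20 = 10.0% |
| 100 mg BID | 2/15 = 13.3% | 3/16 = 18.8% | 2/16 = 12.5% |
| 300 mg BID | 4/19 = 21.1% | 5/20 = 25.0% | 4/20 = 20.0% |

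If 75% is the intended DLT threshold, leaving the subject out overstates the rate by 0.5 to 1.1 percentage points. If 80% is intended, it understates the rate by 3.9 to 5.4 points.

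**After the fix.** With a DLT at less than 80% of cohort-dose doses because of toxicity, no dose count satisfies both k/84 >= 0.80 and k/84 < 0.80, so the gap is empty.

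**The case against.** The strongest reply is that nothing is undefined. Section 4.1.1 does classify the subject: below 80% with no DLT is non-evaluable, and another subject is enrolled. The two thresholds also serve different purposes, one for enough exposure to call a dose safe, the other for toxicity severe enough to limit the dose, and they need not be equal. Under the 75% definition as written, leaving the subject out is the more cautious choice. All of that stands, and a reader should not infer that the plan is silent on such subjects. It does not justify replacing a subject whose shortfall was caused by toxicity.

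Low-grade events also reached the DLT count. Section 5.5.2 speaks of a group that will "review and adjudicate individual high-grade AEs as potentially dose-limiting", but the DLTs in Section 1.4.2 include a Grade 1 erythema and a Grade 2 ataxia. Neither meets a grade criterion in Table 5, so the general criteria or adjudication were catching lower-grade toxicity. That makes an empty gap more plausible.

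The information is not lost either. Every treated subject is in the safety analyses, interruptions and reductions are tabulated, and Section 1.4.2 gives interruptions and reductions as a direct reason for choosing 100 mg BID.

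Finally, the reduction route cannot be carried back to Phase 1 with any precision. Appendix K shows that Table 7 was added in Amendment 5, which also recorded the recommended dose already determined in Phase 1, and that Table 8 was reorganised in Amendment 9. The rules in force during the Phase 1 DLT windows are not visible.

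**Conclusion.** The mismatch is real and is in the current text of both documents. It is a minor point. The 63-67 range assumes that 75% is a count of planned doses; on another basis the range differs. The number of subjects affected is not given and may be zero, and the direction of any effect depends on which threshold was meant.

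Two stronger readings are tempting and are not supported.

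- **A ceiling of about six subjects.** Section 1.1.4 states: "As of 27 FEB 2017, a total of 356 subjects have been enrolled". Taking off the 294 reported for Phase 2 leaves 356 - 294 = 62. Subtracting 19 + 15 + 19 = 53 evaluable and an assumed 3 at 25 mg BID leaves 6. The inputs do not bear this. The 294 come from a safety update limited to subjects with at least one month of data, and that text mixes Phase 2 with combined-phase groups. Section 4.4 says only approximately 62, the dose-level data are described as preliminary, and the 25 mg BID count is not reported. The Phase 1 adverse event percentages in Section 1.4.2 (5 subjects = 4.3%, 2 = 1.7%) imply a denominator of about 117 (5/0.043 = 116; 2/0.017 = 118).
- **A wrong escalation or dose choice.** The documents do not give DLT results by cohort in order of enrolment, and 300 mg BID was the last step in Table 1, so no escalation followed from its rate. No escalation decision or choice of 100 mg BID is shown to be affected.

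**What to change.** Use one threshold on one basis in both rules: Protocol 4.1.1 (and the synopsis text that repeats it) with Table 5, and SAP 3.1 with Table 3. For example, count a DLT when less than 80% of doses at the cohort dose is received because of toxicity, which matches the evaluability rule. Replace a subject as non-evaluable only when the shortfall is not due to toxicity.

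Because Phase 1 is complete, apply this in the clinical study report as a sensitivity check and not as a retrospective redefinition. List each non-evaluable Phase 1 subject with the percentage of doses taken, both at the cohort dose and at any level, and the reason for the shortfall. Then give the DLT rate with any gap subjects counted as DLTs and again as evaluable non-DLTs.

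The cost is wording in two documents and a check of a short list. Planned Listings 2.5.1 (epacadostat dosing), 2.7.4 (DLTs) and 2.7.6 (events leading to interruption, reduction or discontinuation) should supply most of what is needed. SAP Appendix E plans a DLT listing but no table of DLT rates, so the two rates would be a small new output. A reported rate could look slightly less favourable. If no subject falls in the gap, one sentence closes the point.

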**5.5.2. Procedures for Cohort Review and Dose Escalation in Phase 1**

Telephone conferences will be scheduled by the sponsor with Phase 1 investigators in order to review cohort-specific data, overall safety data from prior cohorts (if applicable), and to agree on dose escalation. For additional safety oversight, this group will review and adjudicate individual high-grade AEs as potentially dose-limiting and for guiding the study team on decisions regarding dose escalation and cohort expansion. The same method will be used for reviewing data at the end of Phase 1 to determine the recommended dose for Phase 2.

**5.5.3. Procedures for Safety Review for Phase 2 Expansion Cohorts**

Interim safety analyses are planned for Phase 2 after 20 subjects have been enrolled and treated for 9 weeks, and then every 3 months thereafter. If the following is reported during these reviews, enrollment of subjects would be suspended until the sponsor(s), investigators, and regulatory authorities, if applicable, have determined the appropriate course of action:

- > 40% of subjects have had an AE  $\geq$  Grade 3 that was attributable to the investigational agents.

**5.5.4. Follow-Up for Dose-Limiting Toxicities**

Subjects whose treatment is discontinued because of a DLT must be followed until resolution or stabilization of the DLT event, whichever comes first.

## **5.6. Dose Adjustment of Study Drugs**

### **5.6.1. Planned Dose Adjustments**

Intrasubject dose escalations are not permitted. Subjects will remain on their cohort-assigned dose, or a lower dose if required because of AEs, throughout the treatment and extension portions.

### **5.6.2. Criteria and Procedures for Interruption**

In some circumstances, it may be necessary to temporarily interrupt both study treatments as a result of AEs that may have an unclear relationship to study drug. Any interruptions of > 2 weeks or for LFT abnormalities must be discussed with the medical monitor before resuming treatment. Treatment with both study drugs should be withheld for drug-related Grade 4 hematologic toxicities, nonhematological toxicity  $\geq$  Grade 3 (including laboratory abnormalities), and severe or life-threatening AEs (see [Table 6](#)). [Table 6](#) summarizes the dosing actions for MK-3475 and INCB024360 that must be implemented with the indicated related AEs. [Table 7](#) provides dose modification guidance for epacadostat. Additional information related to dose changes for INCB024360 and MK-3475 and guidance for immune-related toxicities can be found in [Section 5.6.3](#) and for SS in [Section 5.6.5](#).

Except in cases of emergency, it is recommended that the investigator consult with the sponsor's medical monitor (or other representative of the sponsor) before temporarily interrupting therapy for reasons other than Protocol-mandated medication hold. Additionally, the investigator must notify the sponsor's medical monitor and study project manager via email before restarting study drug that was temporarily interrupted because of an AE.

Dosing interruptions are permitted in the case of medical/surgical events or logistical reasons not related to study therapy (eg, elective surgery, unrelated medical events, subject vacation, and/or holidays). Subjects should be placed back on study therapy within 3 weeks of the scheduled interruption, unless otherwise discussed with the sponsor. The reason for interruption should be documented in the subject's study record.

**Table 6: Dose Modification Guidelines for Drug-Related Adverse Events**

Toxicity	Grade	Hold Treatment (Y/N)	Timing for Treatment Restart	Dose/Schedule for Treatment Restart		Discontinue Subject (After Medical Monitor Consultation)
				INCB024360	MK-3475	
Hematologic toxicity	1, 2	No	N/A	N/A	N/A	N/A
	3	Yes	Toxicity resolves to $\leq$ Grade 1 or baseline	Restart at same dose	Restart at same dose and schedule. See Section 5.6.3 for recommendations regarding immune-mediated AEs.	Toxicity does not resolve within 12 weeks of last infusion.
	4	Yes	N/A	N/A	N/A	Permanently discontinue
Nonhematologic toxicity Note: Exception to be treated to similar Grade 1 toxicity: – Grade 2 alopecia – Grade 2 fatigue – Grade 3 rash in the absence of desquamation, no mucosal involvement, does not require systemic steroids, and resolves to Grade 1 within 14 days For additional information regarding AEs with potential immune etiology, see Section 5.6.3 or for subjects with HCC, refer to Appendix J for guidance related to hepatic adverse events.	1	No	N/A	N/A	N/A	N/A
	2	Consider holding for persistent symptoms	Toxicity resolves to $\leq$ Grade 1 or baseline	Restart at same dose	Restart at same dose and schedule. See Section 5.6.3 for recommendations regarding immune-mediated AEs.	Toxicity does not resolve within 12 weeks of last infusion
	3	Yes	Toxicity resolves to $\leq$ Grade 1 or baseline	Restart at 1 dose level lower.	Restart at same dose and schedule. See Section 5.6.3 for recommendations regarding immune-mediated AEs.	Toxicity does not resolve within 12 weeks of last infusion. Permanent discontinuation should be considered for any severe or life-threatening event.
	4	Yes	N/A	N/A	N/A	Permanently discontinue

Note: Subjects who experience a recurrence of the same severe or life-threatening AE at the same grade or greater with rechallenge of the combination should be discontinued from study treatment. For toxicities such as recurrent or intolerant rash with this combination, subjects may have the opportunity to resume treatment with MK-3475 alone with medical monitor approval.

In case toxicity does not resolve to Grade 0 to 1 within 12 weeks after last infusion of MK-3475, study treatment should be discontinued after consultation with the sponsor. With investigator and sponsor agreement, subjects with a laboratory AE still at Grade 2 after 12 weeks may continue treatment in the study only if asymptomatic and controlled. For information on the management of irAEs, see Section 5.6.3.

